7.1.4.6 Response in Non-Measurable Lesions (RECIST 1.1)

While some non-target lesions may actually be measurable, they need not be measured and instead should be assessed only qualitatively.

- Complete Response (CR): Disappearance of all non-target lesions and normalization of tumor marker level. All lymph nodes must be non-pathological in size (< 10 mm short axis).
- Non-CR/Non-PD: Persistence of one or more non-target lesion(s) and/or maintenance of tumor marker level above the normal limits.
- Progressive Disease (PD): Unequivocal progression of existing non-target lesions. (Note: the appearance of one or more new lesions is also considered progression).

When the patient also has measurable disease, to achieve ‘unequivocal progression’ on the basis of non-target disease, there must be an overall level of substantial worsening in non-target disease such that, even in presence of SD or PR in target disease, the overall tumor burden has increased sufficiently to merit discontinuation of therapy.

In the event that the patient has only non-measurable disease, the same general concepts apply as noted above, however, in this instance there is no measurable disease assessment

to factor into the interpretation of an increase in non-measurable disease burden. Because worsening in non-target disease cannot be easily quantified, a useful test that can be applied when assessing subjects for unequivocal progression is to consider if the increase in overall disease burden based on the change in non-measurable disease is comparable in magnitude to the increase that would be required to declare PD for measurable disease (ie, an increase in tumor burden representing an additional 73% increase in ‘volume’ which is equivalent to a 20% increase diameter in a measurable lesion).

7.1.4.7 Immune-Related Response in Non-Measurable Lesions (irRECIST)

At each tumor assessment, the presence of any new, non-measurable lesions is assessed. The presence of such lesions will rule out an overall response of irCR. An increase in the size or number of new, non-measurable lesions does not necessarily imply an overall response of irPD; if these lesions become measurable (≥ 10 mm) at a subsequent tumor assessment, their measurement will at that point start to contribute to the TMTB.

In addition, the response in non-target lesions is defined as follows:

Complete Response (irCR): complete disappearance of all non-target lesions

Stable Disease (irSD): non-target lesions are stable

Progressive Disease (irPD): unequivocal increases in number or size of non-target lesions. To achieve unequivocal progression of non-target lesions, there must be an overall level of substantial worsening of non-target disease that is of a magnitude that the treating physician would feel it is important to change therapy.

NOTE: Equivocal findings of progression of non-target lesions (eg, small and uncertain new lesions; cystic changes or necrosis in existing lesions) should be considered irSD, and treatment may continue until the next scheduled assessment.

7.1.4.8 Overall Response

Overall response will be determined based on RECIST 1.1 criteria and by irRECIST criteria (Table 9). Overall response according to irRECIST is derived from the responses in measurable lesions (based on TMTB) and the presence of any non-measurable lesions.

Table 9 Tumor Response Evaluation: Comparison of RECIST 1.1 and irRECIST

Criteria	RECIST1.1	irRECIST
New measurable lesions (≥ 10 mm)	Always represents PD	Incorporated into tumor burden

Criteria	RECIST1.1	irRECIST
New non-measurable lesions (< 10 mm)	Always represents PD	Does not define progression but precludes irCR
Non-Target lesions	Changes contribute to defining BOR of CR, PR, SD, and PD	Contribute to defining irCR (complete disappearance required)
CR	Disappearance of all lesions	Disappearance of all lesions
PR	≥ 30% decrease in the sum of the longest diameter of all target lesions compared with baseline, in absence of new lesions or unequivocal progression of non-target lesions	≥ 30% decrease in tumor burden compared with baseline
SD	Neither sufficient shrinkage to qualify for PR nor sufficient increase to qualify for PD, taking as reference the smallest sum diameters while on study	Neither a 30% decrease in tumor burden compared with baseline nor a 20% increase compared with nadir can be established
PD	At least 20% increase in sum of diameters of target lesions, taking as reference the smallest sum on study. In addition to the relative increase of 20%, the sum must also demonstrate an absolute increase of at least 5mm. The appearance of one or more new lesions is also considered progression.	At least 20% increase in tumor burden compared with nadir (at any single time point) ^a

irRECIST = immune-related Response Evaluation Criteria in Solid Tumors; BOR = best overall response; CR = complete response; irCR = immune-related complete response; PD = progressive disease; PR = partial response; SD = stable disease;

^a Patients with an initial finding of progressive disease (irPD) before or at the 8-week imaging assessment, but without rapid clinical deterioration, require confirmation of irPD with a second, consecutive scan obtained ≥ 4 weeks from the initiation documentation. Patients will continue to receive study treatment until irPD is confirmed at this later time point. Best overall response (BOR) will therefore include responses occurring at any time before disease progression and after early progression (i.e., within the first 9 weeks of the study).

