7.1.4.5 Immune-Related Response in Measurable Lesions (irRECIST)

In addition to evaluation using RECIST 1.1 criteria, an immune response adaptation of RECIST will be applied to this trial. The essential differences between irRECIST and RECIST criteria are as follows:

- New measurable lesions do not necessarily constitute progressive disease and they should be added into the total tumor burden. New non-measurable lesions do not constitute disease progression but will prevent the determination of an irCR.

- Apparent disease progression should be confirmed after 4 weeks in the absence of symptoms consistent with clinical deterioration.

At baseline, the sum of the longest diameters (SumD) of all target lesions (2 per organ and 5 in total) is measured. At each subsequent tumor assessment, the SumD of the target lesions and of new, measurable lesions (≥ 10 mm [lymph nodes ≥ 15 mm in shortest diameter]; up to 2 new lesions per organ, total 5 new lesions) are added together to provide the total measurable tumor burden (TMTB):

$TMTB = \text{SumD target lesions} + \text{SumD new, measurable lesions}$

Percentage changes in TMTB per assessment time point describe the size and growth kinetics of both old and new measurable lesions as they appear. At each tumor assessment, the response in target and new measurable lesions is defined based on the change in TMTB (after ruling out irPD) as follows:

Complete Response (irCR): complete disappearance of all target and new, measurable lesions, with the exceptions of lymph nodes which must decrease to < 10 mm in short axis

Partial Response (irPR): decrease in TMTB $\geq 30\%$ relative to baseline (see below)

Stable Disease (irSD): not meeting criteria for irCR or irPR, in absence of irPD

Progressive Disease (irPD): increase in TMTB $\geq 20\%$ relative to nadir

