7.1.4.8.1 Best Overall Response (RECIST 1.1)

The best overall response is the best response recorded from the start of the study treatment until the end of treatment taking into account any requirement for confirmation. The patient's best overall response assignment will depend on the findings of both target and non-target disease and will also take into consideration the appearance of new lesions (Table 10).

Table 10 Best Overall Response (RECIST 1.1)

Target Lesions	Non-Target Lesions		Overall Response
	Baseline Lesions	Unequivocal New Lesions	
Baseline (Index) and New Measurable Lesions	CR	No	CR

Target Lesions Baseline (Index) and New Measurable Lesions	Non-Target Lesions		Overall Response
	Baseline Lesions	Unequivocal New Lesions	
CR	Non-CR/Non-PD	No	PR
CR	NE	No	PR
PR	Non-PD or NE	No	PR
SD	Non-PD or NE	No	SD
Not all evaluated	Non-PD	No	NE
PD	Any	Yes or No	PD
Any	PD	Yes or No	PD
Any	Any	Yes	PD

CR = complete response; NE = not evaluable at a particular time point; PR = partial response; SD = stable disease; PD = progressive disease

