7.1.4.8.2 Immune-Related Best Overall Response (irRECIST)

The immune-related best overall response (irBOR) is the best irRC overall response over the study as a whole, recorded between the date of first dose until the last tumor assessment prior to subsequent therapy (including tumor resection surgery) for the individual subject in the study (Table 11). As with the primary definitions of tumor response, early progression (i.e., irPD occurring prior to Week 8) will not preclude an irBOR of irCR, irPR or irSD resulting from the Week 8 assessment. An assessment of irPD at or after Week 8 will preclude a subsequent irBOR of irCR, irPR or irSD. However, any post-progression clinical activity in subjects with irBOR of irPD may be summarized for exploratory purposes.

Table 11 Immune-Related Best Overall Response (irBOR)

Target Lesions Baseline (Index) and New Measurable Lesions	Non-Target Lesions ^a		irRC Overall Response
	Total Measurable Tumor Burden	Baseline Lesions	
irCR	irCR	No	irCR
irCR	irSD	No	irPR
irPR	irCR or irSD	No	irPR
irSD	irCR or irSD	No	irSD

Target Lesions Baseline (Index) and New Measurable Lesions	Non-Target Lesions ^a		irRC Overall Response
	Total Measurable Tumor Burden	Baseline Lesions	
irPD	Any	Yes or No	irPD
Any	Unequivocal Progression	Yes or No	irPD
Any	Any	Yes	irPD

irCR = immune-related complete response; irPR = immune-related partial response; irSD = immune-related stable disease; irPD = immune-related progressive disease

^a Any increase in the size or number of non-measurable lesions does not necessarily imply an overall response of irPD. If these lesions become measurable (≥ 10 mm) at a subsequent assessment, their measurement will at that point start to contribute to the total measurable tumor burden. To achieve unequivocal progression of non-target lesions, there must be substantial worsening in non-target disease that is of a magnitude that the Investigator feels it is important to change therapy. Equivocal findings of progression of non-target lesions (e.g., small and uncertain new lesions; cystic changes or necrosis in existing lesions) should be considered irSD, and treatment may continue until the next assessment.

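### Table 11 scores an unequivocal new non-measurable lesion as irPD, while Section 7.1.4.5 and Table 9 say such a lesion only rules out irCR

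*Combined protocol and SAP*

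**What the plan says.** Four places in the protocol address a new lesion under irRECIST.

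- **Section 7.1.4.5**, listing the essential differences from RECIST: "New non-measurable lesions do not constitute disease progression but will prevent the determination of an irCR". For measurable ones: "New measurable lesions do not necessarily constitute progressive disease and they should be added into the total tumor burden".
- **Section 7.1.4.7**, on new non-measurable lesions: "The presence of such lesions will rule out an overall response of irCR", and "An increase in the size or number of new, non-measurable lesions does not necessarily imply an overall response of irPD". The section separately defines non-target irPD as an unequivocal increase in number or size that amounts to substantial worsening. Equivocal findings, including small and uncertain new lesions, are to be scored irSD.
- **Table 9** (Section 7.1.4.8), irRECIST column for new non-measurable lesions: "Does not define progression but precludes irCR". The RECIST 1.1 column of the same row makes them PD in every case.
- **Table 11** (Section 7.1.4.8.2): the irPR row reads "irPR irCR or irSD No irPR", the irCR and irSD rows also carry No, and the last row reads "Any Any Yes irPD". Footnote a repeats that more or larger non-measurable lesions need not mean irPD, and that equivocal findings are irSD.

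Table 10, for RECIST 1.1, has the same layout and the same final row, ending in PD. There the Yes/No column is headed "Unequivocal New Lesions".

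**The concern.** Section 7.1.4.5 and Table 9 present the handling of new non-measurable lesions as one of the points where irRECIST departs from RECIST 1.1. The last row of Table 11 appears to carry the RECIST 1.1 rule over for those lesions. Section 7.1.4.8 sends the reader to Table 9 for the overall response, Section 7.1.4.8.2 sends the reader to Table 11 for the best overall response, and Section 8 does not say which governs.

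The endpoints exposed are the secondary ones: response rate, 6-month PFS, PFS and duration of response by irRECIST (Section 3.2). Two programmers working from the same scans could classify the same subject differently. The trial is open-label, so a choice made at analysis would be made with results in view.

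**Working it through.** The plan states no figure for this point, so the check compares rules.

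**Step 1: what the Yes/No column in Table 11 means.** Its heading does not survive in the text available for this review. There are three candidates:

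- *New measurable lesions.* These already enter the TMTB in the first column, and Table 9 counts them in tumor burden. An automatic irPD row for them would contradict both.
- *Progression of baseline non-target lesions.* The row directly above already covers this.
- *Unequivocal new lesions*, as in the matching position of Table 10. With measurable ones in the TMTB, the column then acts on new non-measurable lesions.

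Only the third is coherent. It remains an inference from Table 10.

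**Step 2: restrict to the disputed case.** Take an unequivocal new non-measurable lesion, with no 20% TMTB rise and no unequivocal non-target progression. That leaves 3 measurable-burden states (irCR, irPR, irSD) × 2 baseline non-target states (irCR, irSD) = 6 combinations.

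**Step 3: classify each combination both ways.**

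| Measurable burden | Baseline non-target | Table 11 | Section 7.1.4.5 and Table 9 |
|---|---|---|---|
| irCR | irCR | irPD | not irCR, not irPD; a 100% fall meets the 30% threshold, so irPR |
| irCR | irSD | irPD | irPR |
| irPR | irCR | irPD | irPR |
| irPR | irSD | irPD | irPR |
| irSD | irCR | irPD | irSD |
| irSD | irSD | irPD | irSD |

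The two sources disagree in 6 of 6. In four, a responder becomes a progressor. In the two irSD rows the response rate does not change, but a PFS event is created.

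**Step 4: the effect per subject.** Using the planned evaluable numbers in Section 8.2 (31 in Stage 1, 55 in total):

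- Stage 1: 1/31 = 0.032, or 3.2 percentage points.
- Both stages: 1/55 = 0.018, or 1.8 percentage points.

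These are shifts in a simple proportion. With k subjects reclassified the shift is k/31 or k/55; the documents give no basis for k.

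**Step 5: persistence.** Under Section 7.1.4.8.2, irPD at or after Week 8 prevents a later best response of irCR, irPR or irSD. From Week 8 on, a subject scored by the last row of Table 11 therefore cannot be credited with a subsequent response.

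**The case against.** The strongest reply is that the irRECIST section contains enough qualifications to neutralise the row. Much of this is right and limits the point:

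- **Equivocal lesions are protected.** Footnote a and Section 7.1.4.7 score small, uncertain new lesions as irSD. A subject with a 40% fall in TMTB and an equivocal small nodule is irPR under Table 11 too.
- **Section 7.1.4.7 is not categorical.** It says irPD does not necessarily follow, and it allows irPD for an unequivocal increase in number with substantial worsening. Only Section 7.1.4.5 and Table 9 are categorical. The softer wording still does not fit a row that gives irPD without condition, and Table 11 already has a separate row for unequivocal progression.
- **The bar on later response is conditional.** It applies to irPD at or after Week 8; earlier irPD does not preclude response. Table 9 footnote a requires a confirmatory scan for irPD at or before the 8-week assessment without rapid clinical deterioration. A response recorded before the new lesion appeared still counts as best response.
- **The column heading is inferred.** This is fair, but Step 1 leaves no other coherent reading.
- **The primary endpoints are untouched.** The primary objective uses RECIST 1.1 (Section 3.1), and Section 2 names RECIST 1.1 for the response criterion that opens Stage 2.

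A reader might infer that Table 11 turns every new lesion into irPD, or that irRECIST collapses into RECIST 1.1. The documents do not support either. New measurable lesions go into the TMTB, equivocal lesions are exempt, and the confirmation rules remain. What survives is the unequivocal new non-measurable lesion without other progression, which none of these qualifications resolves.

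**Conclusion.** The contradiction stands in that narrow form. For an unequivocal new non-measurable lesion with no 20% TMTB rise and no unequivocal non-target progression, Table 11 gives irPD in all six possible combinations; Section 7.1.4.5 and Table 9 give it in none. Table 11 also sits badly with its own footnote.

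The size is 3.2 points per reclassified subject in Stage 1 and 1.8 points over both stages, on secondary irRECIST endpoints only. A reader might go on to infer that a sizeable share of the irRECIST 6-month PFS rate depends on this choice. The documents do not say how often the case arises, and a subject who progresses on TMTB or dies before six months is a PFS event by then under either rule, so no total effect can be stated.

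The conclusion assumes that the Table 11 column carries the Table 10 heading, which should be confirmed against the original page. The per-subject figures assume that the planned evaluable numbers are the denominators.

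**What to change.** For endpoint derivation, and before data are analysed, reconcile Table 11 with Section 7.1.4.5 and Table 9:

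- Amend the last row so that an unequivocal new non-measurable lesion precludes irCR but does not by itself give irPD.
- Change No to Yes or No in the irPR and irSD rows, and provide for a subject who would be irCR but for the new lesion; by the Table 9 threshold this is irPR.
- Confirm that the column heading refers to unequivocal new non-measurable lesions.
- Keep the irPD rows for TMTB and for unequivocal non-target progression, and keep the Section 7.1.4.7 criterion on increases in number or size.

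The cost is table wording and one programming rule.

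Table 9 footnote a makes continued treatment depend on confirmed irPD, so the same passages bear on treatment continuation. The sponsor must reconcile them for that purpose as well; the change above concerns how endpoints are derived and proposes no clinical rule.

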7.1.4.4 Response in Measurable Lesions (RECIST 1.1)

At baseline, the sum of the longest diameters (SumD) of all target lesions (up to 2 lesions per organ, up to total 5 lesions) is measured. At each subsequent tumor assessment, the SumD of the target lesions and of new, measurable lesions (≥ 10 ; up to 2 new lesions per organ, total 5 new lesions) are added together to provide the total measurable tumor burden (TMTB):

TMTB = SumD target lesions + SumD new, measurable lesions

Percentage changes in TMTB per assessment time point describe the size and growth kinetics of both old and new measurable lesions as they appear. At each tumor assessment, the response in target and new measurable lesions is defined based on the change in TMTB.

- Complete Response (CR): Disappearance of all target lesions. Any pathological lymph nodes (whether target or non-target) must have reduction in short axis to < 10 mm.
- Partial Response (PR): At least a 30% decrease in the sum of diameters of target lesions, taking as reference the baseline sum diameters.
- Progressive Disease (PD): At least a 20% increase in the sum of diameters of target lesions, taking as reference the smallest sum on study (this includes the baseline sum if that is the smallest on study). In addition to the relative increase of 20%, the sum must also demonstrate an absolute increase of at least 5 mm. (Note: the appearance of one or more new lesions is also considered progression).
- Stable Disease (SD): Neither sufficient shrinkage to qualify for PR nor sufficient increase to qualify for PD, taking as reference the smallest sum diameters while on study.

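### irPD omits the 5 mm minimum that RECIST 1.1 PD carries, so below a 25 mm nadir sum irRECIST can score progression on target growth that RECIST 1.1 scores as stable

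*Combined protocol and SAP*

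**What the plan says.** Two response systems are applied to the same scans. RECIST 1.1 serves the primary objective, and irRECIST serves a secondary objective with the same two measures, response rate and 6-month PFS (sections 3.1 and 3.2). Duration of response is a further secondary endpoint under both.

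- **RECIST 1.1 PD.** Section 7.1.4.4 requires a 20% increase over the smallest sum, and adds that "the sum must also demonstrate an absolute increase of at least 5 mm". The RECIST column of Table 9 repeats it: "In addition to the relative increase of 20%, the sum must also demonstrate an absolute increase of at least 5mm". New lesions count at once: "The appearance of one or more new lesions is also considered progression".
- **irPD.** Section 7.1.4.5 has "Progressive Disease (irPD): increase in TMTB" of 20% or more relative to nadir, where TMTB is the total measurable tumour burden. The irRECIST column of Table 9 has "At least 20% increase in tumor burden compared with nadir (at any single time point"). Neither gives a minimum in millimetres.
- **Declared differences.** Section 7.1.4.5 introduces its list with "The essential differences between irRECIST and RECIST criteria are as follows" and names two: the handling of new lesions, and confirmation of apparent progression after 4 weeks. A lower growth threshold is not on the list.
- **Confirmation.** Footnote a to the Table 9 irPD cell says that subjects with irPD before or at the 8-week scan, without rapid clinical deterioration, "require confirmation of irPD with a second, consecutive scan obtained" at least 4 weeks later.

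**The concern.** irRECIST is there to avoid calling progression too soon. Section 5.10 explains that a response may follow an initial rise in tumour burden, and section 7.1.4.7 scores equivocal non-target findings as irSD. A target-lesion threshold that is easier to cross than the RECIST 1.1 threshold works the other way.

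The affected range can be reached. One measurable lesion is enough for entry, and 10 mm suffices on spiral CT or MRI (inclusion criterion 5 and section 7.1.4.2). Because the reference is the nadir, responders can also move into it: a baseline sum of 35 mm that falls by 30% leaves 35 × 0.70 = 24.5 mm. These are the subjects who determine duration of response.

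At stake is how the irRECIST response rate, 6-month PFS and duration of response are read. With at most 55 subjects, a few low-burden subjects scored irPD on a rise of 2 to 4 mm would shift a rate. Part of any gap from the RECIST 1.1 results would then come from an undeclared change of threshold.

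**Working it through.** **Step 1: where the rules part.** With nadir sum S, irPD needs a rise of 0.20 × S. RECIST 1.1 target-lesion PD needs the larger of 0.20 × S and 5 mm. They meet at S = 5/0.20 = 25 mm.

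| Nadir sum (mm) | Rise for irPD (mm) | Rise for RECIST 1.1 PD (mm) |
|---|---|---|
| 10 | 2.0 | 5 (50%) |
| 12 | 2.4 | 5 (42%) |
| 15 | 3.0 | 5 (33%) |
| 20 | 4.0 | 5 (25%) |
| 24 | 4.8 | 5 (21%) |
| 25 | 5.0 | 5 (20%) |
| 30 | 6.0 | 6 (20%) |

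Example: a single target lesion goes from 12 mm to 15 mm. The rise is 3/12 = 25%, so irPD is met. It is 3 mm, under 5 mm, so RECIST 1.1 gives SD.

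**Step 2: reading error at one scan.** The documents give neither a reading error nor a tumour-size distribution, so the SD is an assumption shown over a range. Take a truly stable sum S read at baseline (x0) and at one follow-up (x1), each with independent normal error of SD s. False irPD occurs when x1 - 1.2·x0 ≥ 0, a quantity with mean -0.2·S and SD s·√(1 + 1.44) = 1.562·s. For small sums, false RECIST 1.1 PD occurs in effect when x1 - x0 ≥ 5, where the difference has SD 1.414·s.

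- S = 10 mm, s = 1 mm: irPD z = 2/1.562 = 1.28, about 10%. RECIST 1.1 z = 5/1.414 = 3.54, about 0.02%.
- S = 20 mm, s = 1 mm: irPD z = 4/1.562 = 2.56, about 0.5%. RECIST 1.1 stays at about 0.02%.
- S = 10 mm, s = 2 mm: irPD z = 2/3.124 = 0.64, about 26%. RECIST 1.1 z = 5/2.828 = 1.77, about 3.9%.

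Simulation with 400,000 subjects gives the same values. A confirmatory scan lowers the irPD figure for S = 10 mm from 10.1% to 3.9% at s = 1 mm, and from 26.0% to 14.1% at s = 2 mm.

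**Step 3: three scans.** Imaging at Week 8 of each 9-week cycle gives scans at Weeks 8, 17 and 26, the span of the 6-month PFS rate. The simulation (200,000 subjects per row) uses one truly stable lesion with true size log-uniform on 8-15 mm, measured at 10 mm or more at entry, and a running nadir. The table gives the share ever scored falsely as progression.

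| Assumed SD (mm) | irPD, unconfirmed | irPD, only Week 8 confirmed | irPD, every one confirmed | With 5 mm floor, unconfirmed | With floor, confirmed |
|---|---|---|---|---|---|
| 0.5 | 0.6% | 0.6% | 0.1% | 0% | 0% |
| 1.0 | 21% | 19% | 7% | 0.1% | 0% |
| 1.5 | 44% | 41% | 21% | 3% | 0.4% |

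**Step 4: more tumour.** At SD 1.5 mm per lesion, two lesions of 8-30 mm give 8.6% without the floor and 7.5% with it, unconfirmed. Three lesions of 10-30 mm start at a sum of at least 30 mm, and the two rules give the same rate, about 2.5%. The effect is confined to low tumour burden.

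**Step 5: confirmation.** Section 7.1.4.5 and the tumour-imaging footnote to the Schedule of Events (6.1) ask for confirmation without limiting it to the first scan. Footnote a to Table 9 covers only irPD up to the 8-week scan. Section 7.1.4.8.2 closes best overall response on irPD at or after Week 8 and does not mention confirmation. Which column of the Step 3 table applies therefore depends on which passage governs.

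**The case against.** The strongest reply is that the difference is visible and may be intended. Table 9 prints the two PD rules side by side, section 7.1.4.5 states the same irPD threshold, and nothing in the documents says that irRECIST must carry the 5 mm. It can be added that the affected group is narrow, that all measurable lesions become targets up to five (section 7.1.4.3), that irPD is subject to confirmation, and that section 8.3 plans no formal comparison of the two systems.

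Much of this stands. This is not a contradiction between two statements of irPD, the number of low-burden subjects is unknown, and confirmation at least halves the false-irPD rates in the Step 3 table. What remains is that the list of essential differences omits a change that makes irRECIST the stricter system on small target growth, and no reason is given.

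Two stronger readings are tempting, and the documents do not support them.

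- A reader might infer that irPD will often be called on measurement noise. No reading error or size distribution is given. The rate for one small lesion runs from under 1% to 44% as the assumed SD goes from 0.5 to 1.5 mm.
- A reader might infer that irRECIST calls progression earlier in general. When a new lesion appears, RECIST 1.1 calls PD at once. irRECIST adds a new measurable lesion to the burden, and for a new non-measurable one Table 9 says "Does not define progression but precludes irCR" (the last row of Table 11 reads differently). In that setting irRECIST is usually the later of the two.

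One further objection shapes the fix. Footnote a links continued treatment to confirmation of irPD, so rewording irPD without restriction could change clinical management.

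**Conclusion.** The point holds within limits. That the 5 mm minimum is absent from both irPD definitions, and that the break-even is 25 mm, follows from the text and arithmetic alone. For target-lesion growth without new lesions below that nadir sum, a subject can be irPD while still SD under RECIST 1.1.

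How many subjects this would misclassify is not known. The simulated rates rest on assumed SDs, independent normal errors and a single lesion of 8-15 mm. They show that the effect may be negligible or substantial in low-burden subjects, and that it is small once there are two or more lesions.

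The reach is limited to the secondary irRECIST endpoints: response rate, 6-month PFS and duration of response. The RECIST 1.1 primary endpoints and the Stage 1 gate are not affected. The change is worth making because it is cheap and removes an artefact from named secondary endpoints.

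**What to change.** For derivation of the irRECIST endpoints, score irPD on TMTB as an increase over nadir of at least 20% and at least 5 mm, at the first and at the confirmatory scan. State this in section 7.1.4.5 and in the irRECIST PD cell of Table 9, marked as applying to endpoint derivation. If the sponsor intends irPD to have no floor, add that to the listed differences in section 7.1.4.5 with the reason.

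The cost is one clause in two places, with no new scans, data or subjects. The downside is that a small true progression in a low-burden subject may be scored one scan later, which RECIST 1.1 already accepts. Target-lesion thresholds at nadir sums of 25 mm or more do not change.

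Separately, the passages on confirmation must be reconciled: section 7.1.4.5 and the imaging footnote in section 6.1 on one side, Table 9 with its footnote a and section 7.1.4.8.2 on the other. Because footnote a also concerns treatment, that is for the sponsor to settle. The scoring change proposes no rule for stopping or continuing treatment.
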